#### **7.4.6 Physical examination**

The normality and abnormality before and after the treatment are described.

#### **7.4.7 Concomitant medications**

The usage and frequency of use of each drug for concomitant medications during the study period (including WBC-elevating drugs and platelet-elevating drugs used within 14 days before screening, any changes in the concomitant medications during the screening period, new concomitant medications after screening, medications for AEs, and concomitant medications during the follow-up period) are summarized.

## 7.5 Interim Analysis

None

## 7.6 Other Analyses

### 7.6.1 Subgroup analysis

Subgroup analyses are performed for the primary efficacy endpoint according to the following factors, and the forest plot on HR is produced:

Age ( $\leq 65$  years old,  $> 65$  years old)

ECOG PS (0, 1)

Presence of vascular invasion (yes, no)

Presence of extrahepatic metastasis (yes, no)

Presence of vascular invasion and/or extrahepatic metastasis (yes, no)

Treatment with sorafenib (yes, no)

Previous systemic treatment line(s) (one line,  $\geq$  two lines)

HBV (positive, negative)

Alpha-fetoprotein (AFP  $< 400\mu\text{g/L}$ ,  $\geq 400\mu\text{g/L}$ )

Alpha-fetoprotein (AFP  $< 200 \mu\text{g/L}$ ,  $\geq 200 \mu\text{g/L}$ )

Child-Pugh score (Grade A, Grade B)

BCLC stage (B, C)

Previous liver transplant (yes, no)

### 7.6.2 Other Analyses

To assess the balance of new anti-tumor treatments between groups during the study, new anti-tumor treatments (including systemic treatment and local treatment) are summarized. In addition, the new anti-tumor treatments are classified, and the subgroup analyses of OS are performed. New anti-tumor treatments are classified into chemotherapy, targeted therapy, immunotherapy, and local treatments (TACE, surgery, ablation therapy, and radiotherapy). New anti-tumor treatments do not include traditional Chinese medicine and immunomodulators. Before database locking, classification of new anti-tumor treatments is finally determined and archived.

Other sensitivity analyses of OS include:

- 1) The OS of two groups will be compared by the Wilcoxon test and Max-Combo method.
- 2) The survival time of subjects are censored at the start of new anti-tumor treatments.
- 3) In the OS analysis, some subjects who have received some other types of anti-tumor treatments (which may have a major impact on survival) during the study are excluded, such as subjects with subsequent PD1/PD-L1 treatments will be excluded.
- 4) Rank-preserving structural failure time model (RPSFTM) proposed by Robins and Tsiatis: The OS of subjects who have received apatinib (or other targeted therapies) during the study anti-tumor treatment is adjusted using the RPSFTM method. This analysis will be based on the population defined by FAS and the sensitivity analysis method 2), respectively.
- 5) IPCW method proposed by Robins and Finkelstein: Using the IPCW method to analyze the HR between the treatment group and control group, with reference to relevant medical literature, the baseline variables and time-related variables are planned to be considered in the IPCW model including ECOG PS, age, gender, presence of extrahepatic metastasis, number of line(s) of past treatment, BCLC grade, etc. If necessary, the duration of study drug exposure, and liver function parameters (such as ALT, AST, and bilirubin) may also be included. The bootstrap method is used to sample from the treatment group and control group, and the 95% CI of the HR is estimated.
- 6) The two-stage method proposed by Latimer et al.: Use the two-stage method to adjust the OS of the subjects receiving the new anti-tumor treatment in the treatment group and control group, respectively. If necessary, relevant variables are included in the two-stage model (see the variables to be included in the IPCW method).

In addition, the stratification factors for randomization in the OS analysis in Section 7.3 will be based on the stratification information in the subject randomization system unless otherwise specified. If the stratification factor information in the randomization system and EDC clinical database are inconsistent (the stratification information in the randomization system is incorrect) for some subjects, their stratification information in the EDC clinical database will be used for the sensitivity analysis.

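### SAP 7.6.2: the OS subgroups by later therapy and the exclusion in item 3 are not randomised comparisons, and, read literally, the second RPSFTM run in item 4 has no switching left to adjust for

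*SAP*

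**What the plan says.** SAP 7.6.2 first tabulates new anti-tumor treatment by arm to check balance. It then adds: "In addition, the new anti-tumor treatments are classified, and the subgroup analyses of OS are performed". The classes are chemotherapy, targeted therapy, immunotherapy and local treatment. The sentence does not say whether the subgroups compare arms. The baseline subgroups of 7.6.1 evidently do: "Subgroup analyses are performed for the primary efficacy endpoint according to the following factors, and the forest plot on HR is produced".

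The numbered sensitivity analyses of OS include:

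- Item 2: "The survival time of subjects are censored at the start of new anti-tumor treatments".
- Item 3: "some subjects who have received some other types of anti-tumor treatments (which may have a major impact on survival) during the study are excluded", with one example given: "such as subjects with subsequent PD1/PD-L1 treatments will be excluded".
- Item 4: "The OS of subjects who have received apatinib (or other targeted therapies) during the study anti-tumor treatment is adjusted using the RPSFTM method". It continues: "This analysis will be based on the population defined by FAS and the sensitivity analysis method 2), respectively".
- Item 5, IPCW: "the baseline variables and time-related variables are planned to be considered in the IPCW model including ECOG PS, age, gender, presence of extrahepatic metastasis", plus further variables. Progression is not named and the censoring event is not stated.

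The classification of later therapies is settled and archived before database lock. Nothing similar is said about which therapies trigger exclusion in item 3. The primary analysis in SAP 7.3.1 is the stratified log-rank test in the FAS.

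Protocol 4.6 bars other anti-tumor treatment before PD. For patients withdrawn for toxicity, however, the follow-up rules in Protocol 4.6 and 9.2 and in note (12) of the Schedule of Activities foresee that new treatment may start before PD.

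**The concern.** To be counted as a recipient of later therapy, a patient must live long enough to start it. If apatinib delays PD, it delays that start, so apatinib recipients have survived a longer qualifying period than placebo recipients. An HR among recipients can then fall below 1 with no effect on OS. Earlier starts after toxicity withdrawal, if commoner on apatinib, push the other way.

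Item 3 has the mirror-image problem. It removes patients who are long-lived by selection, and if it removes more of them from one arm, the remaining arms are no longer comparable. Because the list is open, the exclusion could also be chosen after the data are seen.

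RPSFTM works on time lived after switching. Item 2 censors at the start of new treatment, and targeted therapy is one of the listed classes, so no such time is left in the item 2 data.

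These analyses are the SAP's answer to whether later therapy explains the OS result. If they depart from 1 under the null, they can appear to confirm or to contradict the primary result when they do neither.

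**Working it through.** **1. The design figure, to show what is not affected.** 7.6.2 states no figure of its own. For OS, HR = 6/8.5 = 0.706, two-sided alpha 0.05, power 80%, 2:1. Deaths = (1.960 + 0.842)² / [(2/3)(1/3)(ln 0.706)²] = 7.85 / (0.2222 × 0.1213), about 292. With event probability 0.893 (exponential survival, 12-month accrual, 36 months in total, 15% loss over the study), N = 292/0.893 = 327, within 1.2% of the stated 331. Power at 312 deaths = Φ(√(312 × 0.2222 × 0.1213) − 1.960) = 0.826. Nothing in 7.6.2 enters this.

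**2. Recipient subgroup: inputs.** Median time to PD on apatinib is 3.3 months (750 mg TTP, Protocol 1.5.7). For placebo:

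- 2.8 months, the placebo PFS of the sorafenib trial in Protocol 1.2.2;
- as an extreme, 1.4 months, the 42-day placebo PFS of the gastric trial in Protocol 1.5.5.

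Both placebo figures are PFS, which counts deaths; 3.3 is a TTP. Null median OS is 6 months in both arms. Later therapy is inert and starts 1 month after PD (assumed).

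**3. Recipient subgroup by hand.** Take PD and death as independent and exponential. Among patients alive at the start of later therapy, time to PD has rate ln2/m + ln2/6, where m is the median time to PD. Remaining life then averages 6/ln2 = 8.66 months in either arm. Mean OS of recipients, ignoring the data cut-off:

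- m = 1.4: 1/(0.495 + 0.116) + 1 + 8.66 = 11.3 months
- m = 2.8: 1/(0.248 + 0.116) + 1 + 8.66 = 12.4 months
- m = 3.3: 1/(0.210 + 0.116) + 1 + 8.66 = 12.7 months

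With no OS effect, apatinib recipients appear to live 1.4 months longer (1.4 v 3.3) or 0.3 months longer (2.8 v 3.3).

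**4. Recipient subgroup by simulation.** 390 patients, 2:1, 24-month accrual (assumed), cut at the 312th death, 40% take-up in both arms (assumed), 8000 trials per setting. ρ is the assumed PD–survival correlation. Nominal one-sided error is 2.5%; the FAS gives HR 1.00, error 2.4%.

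| Median PD, placebo v apatinib | Setting | Recipient HR | One-sided error |
|---|---|---|---|
| 1.4 v 3.3 | no scans, ρ 0 | 0.83 | 11.7% |
| 1.4 v 3.3 | protocol scans, ρ 0.5 | 0.87 | 7.3% |
| 1.4 v 3.3 | protocol scans, ρ 0.7 | 0.89 | 6.2% |
| 2.0 v 3.3 | protocol scans, ρ 0.5 | 0.92 | 4.9% |
| 2.8 v 3.3 | protocol scans, ρ 0.5 | 0.97 | 3.2% |
| 3.3 v 3.3 | protocol scans, ρ 0.5 | 1.00 | 2.8% |

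A repeat run gave 0.84 (first row) and 0.89 (second row); I quote 0.84 to 0.89 for this contrast.

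Adding toxicity withdrawal with early later therapy (apatinib v placebo, ρ 0.5): at 1.4 v 3.3, rates of 6% v 0% give 0.90 and 15% v 5% give 0.93. At 2.8 v 3.3 the sign reverses: 1.02 at 15% v 5% and 1.06 at 25% v 5%. The 6% is 3 of 51 (Protocol 4.5.2 and 1.5.7); the other rates are assumptions.

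**5. Item 3.** If a share p of an arm with mean OS 8.66 is removed, and those removed average 11.3, the remainder averages (8.66 − 11.3p)/(1 − p).

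- Apatinib 8%, placebo 17%: 8.43 v 8.12, ratio 8.12/8.43 = 0.96.
- Apatinib 14%, placebo 28%: 8.23 v 7.63, ratio 0.93.
- Equal p: ratio 1.

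These are ratios of means, so only a guide to the HR. Simulation with start linked to PD (4000 trials, ρ 0 and 0.5; uptake apatinib v placebo) gives:

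- 2% v 5%: 0.99
- 8% v 17%: 0.960 and 0.955
- 14% v 28%: 0.920 and 0.913
- 8% v 8%: 1.016 and 1.008
- 17% v 8%: 1.108 and 1.083

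The start-time model matters. With starts spread over months 2 to 8 and null median OS 7 months, the 8% v 17% and 14% v 28% contrasts give 0.93 and 0.87.

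**6. Item 4.** RPSFTM rebuilds untreated time as U(ψ) = T_off + exp(ψ) × T_on. For a placebo patient who switches, T_on is the time after switching. Under item 2 it is zero for everyone, so U does not depend on ψ. In an illustrative placebo arm, mean U at ψ = −0.5, 0, 0.5 is 7.4, 8.6 and 10.6 months in the FAS, but 5.6 at all three under item 2. Without re-censoring, the run returned exactly the item 2 HR in 1600 of 1600 trials. With placebo re-censoring it differed in 99.5% of trials, but slightly (median 0.016, maximum 0.08), and it still adjusts for no switching.

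The FAS run assumes one common effect for apatinib and other targeted therapies. At a true HR of 0.71 it gives 0.72 if later targeted therapy has apatinib's effect, 0.66 if it is inert and 0.77 if it is stronger.

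**7. Items 2 and 5.** Under the null, item 2 gives 0.97 to 1.05, and IPCW with progression in the weights 0.99 to 1.00. The IPCW result is partly built in, because uptake in the simulation depends on progression.

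**The case against.** These are other and sensitivity analyses; no alpha, power or success criterion rests on them. That stands, and it limits the weight of the point. A reader might infer that the primary OS result is at risk. It is not.

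The 1.4 v 3.3 contrast sets a gastric-cancer PFS against an HCC TTP. That stands, so 0.84 to 0.89 is an extreme. The 2.8 figure is imperfect too: it is also a PFS, from the placebo arm of a different trial, and Protocol 1.2.2 attaches a 73% increase to 5.5 v 2.8 although 5.5/2.8 = 1.96. A reader might also infer that the bias always favours apatinib. The toxicity-withdrawal route in the protocol shows that it need not.

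Two-fold uptake differences in a double-blind trial are unsupported. That also stands. If item 3's list covered all later therapy, the most extreme delay alone would give uptake of 18% v 26% and HR 0.96, or 0.997 with median OS 8.5 months. Item 3 is therefore not biased as a matter of course.

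Item 4 speaks of a population, whereas item 2 is a censoring rule and item 3 is the item that removes patients. A wrong cross-reference is plausible. It still has to be corrected, and if item 3 was meant, the run inherits item 3's selection. The tempting claim that this run must equal the item 2 HR holds only without re-censoring.

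Some protection exists. The therapy classes are archived before lock, IPCW and two-stage analyses are planned, and item 5's variable list is open, so progression is not ruled out. None of this closes item 3's list or labels the subgroups.

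**Conclusion.** The point holds in a limited form. The later-therapy OS subgroups and item 3 are not randomised comparisons, and the SAP does not say so. With no OS effect, the recipient HR is about 0.97 at 2.8 v 3.3 months to PD, 0.84 to 0.89 at the extreme, and can exceed 1 when early therapy after toxicity withdrawal is commoner on apatinib. Item 3 is near 1 with equal uptake, about 0.95 to 0.96 at 8% v 17% when later therapy follows PD, and 0.87 to 0.92 at 14% v 28%. Uptake, take-up, correlation and most toxicity rates are assumptions, since the documents give none. If the subgroups were meant as within-arm description, the recipient figures do not apply, but the SAP should say so.

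That item 4's second run corrects for no switching follows from the literal text and needs no assumption about uptake. The documents do not support going further, to barring every HR from these analyses or making IPCW the main later-therapy analysis; those are preferences.

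**What to change.** 1. Keep the tabulation of later therapy by arm. Label the later-therapy OS subgroups and item 3 as exploratory, non-randomised output that can neither support nor contradict the primary result, and state whether the subgroups compare arms.
2. Replace item 3's open wording with a closed list of therapies, archived before unblinding.
3. Run RPSFTM on the FAS only, with re-censoring and a caveat on the common-effect assumption for apatinib and other targeted therapies. Correct or delete the reference to method 2.
4. In the planned IPCW, state the censoring event and include time-varying progression in the weights. Read item 2's unweighted censoring beside it.

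The cost is SAP wording and a less prominent simple exclusion HR. IPCW remains limited: after the 28-day visit, survival follow-up is monthly telephone contact (Protocol 4.9) with no scheduled ECOG or liver values, so the weights must rest on baseline data, progression and the last visit values.

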## **8 STATISTICAL ANALYSIS SOFTWARE**

Jiangsu Hengrui Pharmaceuticals Co., Ltd. is responsible for the data management, and the Department of Biostatistics, School of Public Health, Nanjing Medical University undertakes the statistical analysis of this study. All statistical analyses will be performed using SAS 9.4.

## 10 ATTACHED TABLES

### Appendix 1. Classification table of protocol deviations

Class	Sub-Class	Description of Protocol Deviation	Grade
1-Inclusion/Exclusion Criteria	Eligibility	Not meet a certain inclusion criterion, and/or not meet a certain exclusion criterion	Critical
1-Inclusion/Exclusion Criteria	Eligibility	Misunderstanding of the inclusion/exclusion criteria causes the subject enrollment not meeting the protocol requirements	Critical
2-Informed Consent	Informed consent criteria	The subject has been randomized or started treatment with the study drug before signing the informed consent form	Critical
2-Informed Consent	Informed consent criteria	The subject signs the informed consent form after starting any study-related procedures	Critical
2-Informed Consent	Informed consent criteria	The subject signs an incorrect version of the informed consent form (the latest version is not signed)	Critical
2-Informed Consent	Informed consent criteria	The contact information of the ethics committee or study site is not shown or recorded in the informed consent form	Major
2-Informed Consent	Informed consent criteria	The informed consent form is not dated (including by the subject and/or the investigator)	Major
2-Informed Consent	Informed consent criteria	The informed consent process is not recorded or the record is incomplete	Major
2-Informed Consent	Informed consent criteria	The informed consent procedure is not followed	Critical
2-Informed Consent	Informed consent criteria	The investigator who signs the informed consent form is not in the authorization form or is not authorized	Major
3-Visit Schedule	Criteria for visit schedule	Items scheduled for the visits of the treatment period are not carried out: physical examination, vital sign measurement, quality of life scoring, and ECOG scoring	Minor
3-Visit Schedule	Criteria for visit schedule	Items scheduled for the visits of the treatment period are not carried out: except for physical examination and/or vital sign measurement, quality of life scoring, and ECOG scoring	Major
3-Visit Schedule	Criteria for visit schedule	The first imaging examination after treatment and assessed as PD is carried out beyond the time window	Major
3-Visit Schedule	Criteria for visit schedule	The image examinations other than the ones described above are carried out beyond the time window, or the number of image examinations is more than required	Minor
3-Visit Schedule	Criteria for visit schedule	The imaging examination is not done, or the examination method or technique is inconsistent with that at baseline	Critical
3-Visit Schedule	Criteria for visit schedule	The end-of-treatment visit/safety visit is carried out beyond the time window	Minor
3-Visit Schedule	Criteria for visit schedule	The end-of-treatment visit/safety visit is not done, or there are missing examination items	Major
3-Visit Schedule	Criteria for visit schedule	The survival follow-up is carried out beyond the time window/is missing	Minor

Class	Sub-Class	Description of Protocol Deviation	Grade
3-Visit Schedule	Criteria for visit schedule	Other than those mentioned above, the subject has not conducted the visit as required by the protocol or has not completed the examination and other procedures required for the visit	Depends on the situation (minor or major)
4-Subject Diary	Criteria for study procedures	Less than 80% of the diary card is completed	Minor
4-Subject Diary	Criteria for study procedures	The subject has not brought the diary card to the study site	Major
5-Concomitant Medications	Criteria for concomitant medications	The subject has used a drug prohibited by the trial protocol	Depends on the situation (major or critical)
6-Subject Discontinuation	Criteria for study procedures	The subject meets the criteria for study withdrawal or discontinuation, but the subject has not discontinued the study	Critical
6-Subject Discontinuation	Criteria for study procedures	Discontinues the study drug but does not follow the protocol requirements	Major
7-Study Drugs	Criteria for study procedures	No drug is administered within 48 h after randomization	Minor
7-Study Drugs	Criteria for study procedures	Cases that the storage conditions of apatinib exceed the requirements for a short period of time that does not affect the quality of the drug according to the requirements on the instructions for the storage and use of apatinib	Major
7-Study Drugs	Criteria for study procedures	Cases that the sponsor shall be contacted immediately according to the requirements on the instructions for the storage and use of apatinib	Critical
7-Study Drugs	Compliance to study drugs	Missed dose or overdose of the study drug	Depends on the situation (major or critical)
7-Study Drugs	Compliance to study drugs	The total duration of drug interruption during each treatment cycle exceeds 2 weeks	Critical
7-Study Drugs	Compliance to study drugs	The subject is given a drug to be used by other group	Critical
7-Study Drugs	Criteria for study procedures	The study site or the subject has discarded the bottle of used drug Discrepancies in the inventory of the study drugs	Minor
7-Study Drugs	Other criteria	No continuous temperature records	Major
7-Study Drugs	Compliance to study drugs	In addition to the above, other non-compliance with the use of the study drugs	Depends on the situation (minor or major)
8-Safety Monitoring	SAE	The report of SAEs has not met the time limit required by GCP or related regulations	Critical
8-Safety Monitoring	Review of safety reports	The investigator has not reviewed and signed the safety reports of subjects in time	Major

Class	Sub-Class	Description of Protocol Deviation	Grade
8-Safety Monitoring	AESIs	Incorrect and inappropriate reporting time of AEs	Critical
9-Study Procedures	Management criteria	The responsibility authorization form has not been updated before the start of the study procedures	Minor
9-Study Procedures	Criteria for study procedures	The study operation of the investigator has exceeded the scope of authorization	Major
9-Study Procedures	Management criteria	Non-compliance with other study-related procedures in addition to the above-mentioned clinical trial protocol and drug manual.	Depends on the situation
9-Study Procedures	Criteria of ethical approval	Use study-related documents that are not ethically approved	Critical
9-Study Procedures	Monitoring of entire study by principal investigator	The monitoring is insufficient, especially in terms of the lack of evidence for the monitoring by the principal investigator regarding the safety of subjects	Major
9-Study Procedures	Criteria for source documents	The study site has changed the placement location of the source records of subjects without notifying the clinical research associate (CRA) or providing the CRA with access rights; or the source records are stored at the study site without giving the CRA sufficient rights to access the source records (including HIS/LIS) (per ICH GCP R2 4.1.4, the investigator/study site shall allow the sponsor's monitoring agency to conduct monitoring and verification.)	Major
9-Study Procedures	Randomization procedures	Error in information of randomized stratification	Major

## Appendix 2. Adverse events of special interest

Adverse Event of Special Interest	Preferred Terms of AE
Hypertension	Blood pressure increased
Hypertension	Hypertension
Proteinuria	Protein urine present
Proteinuria	Urine protein
Proteinuria	Proteinuria
Hand-and-Foot Syndrome	Palmar-plantar erythrodysesthesia syndrome
Hemorrhage	Upper gastrointestinal hemorrhage
Hemorrhage	Gastrointestinal hemorrhage
Hemorrhage	Gingival bleeding
Hemorrhage	Anal hemorrhage
Hemorrhage	Hematochezia
Hemorrhage	Melena
Hemorrhage	Mouth hemorrhage

Adverse Event of Special Interest	Preferred Terms of AE
Hemorrhage	Mucosal hemorrhage
Hemorrhage	Subcutaneous hemorrhage
Hemorrhage	Purpura
Hemorrhage	Cerebral hemorrhage
Hemorrhage	Brain stem hemorrhage
Hemorrhage	Pharyngeal hemorrhage
Hemorrhage	Bronchial hemorrhage
Hemorrhage	Hemoptysis
Hemorrhage	Epistaxis
Hemorrhage	Hepatic hemorrhage
Hemorrhage	Scleral hemorrhage
Hemorrhage	Vaginal hemorrhage
Electrocardiogram QT prolonged	QT interval prolonged
White blood cell count decreased	White blood cell count decreased
White blood cell count decreased	Leukopenia

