4.5.2 Dose

Treatment group: Apatinib, 750 mg, q.d.; The dose can be reduced according to toxicity, with the first reduction to 500 mg, q.d., and the second reduction to 250 mg, q.d.; each treatment cycle contains 28 days.

Placebo group: Placebo, q.d. Each treatment cycle contains 28 days.

Considerations for the use of 750 mg in the treatment group:

1. According to the phase I PK data, the C_{max} and AUC of the 850 mg group were both higher than those of the 750 mg group, and it was speculated that the toxicity of the 850 mg group might be higher than that of the 750 mg group;
2. According to the phase II study of apatinib in HCC, the efficacy of the 850 mg group was comparable to that of the 750 mg group (TTP, OS; the DCR in the 850 mg group was slightly higher than that in the 750 mg group); 9 patients in the 850 mg group withdrew from the study due to adverse events with the duration of treatment less than 1 cycle (including 4 cases of gastrointestinal hemorrhage), while 3 patients in the 750 mg group withdrew from the study due to adverse events with the duration of treatment less than 1 cycle (no hemorrhage). Considering that the primary endpoint of phase III trial is OS, the dose of 750 mg, which showed better tolerability in HCC patients, is selected for the study.

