8.3.3 Management of gastrointestinal hemorrhage

Gastrointestinal hemorrhage, including fecal occult blood (++) and above, hematemesis or bloody stool, should be given active symptomatic treatment. Patients with upper gastrointestinal hemorrhage should be fasted and given acid suppression, gastric mucosal protection, hemostasis (transamin, reptilase, etc.), as well as octreotide if necessary; patients with lower gastrointestinal hemorrhage should be given hemostasis, blood transfusion and supportive care, etc.; for those whose bleeding cannot be controlled, assistance from the surgery department should be requested.

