## 7.4 Safety Evaluation

### 7.4.1 Adverse events

AEs are encoded according to the current MedDRA 21.0 and then processed in statistical analysis.

The incidences of AEs, treatment-related adverse events (TRAEs), AEs leading to drug interruption, dose reduction, and drug discontinuation, and SAEs are summarized. If multiple AEs occurred in the same subject, the number of subject is counted as one when calculating the incidence; if a subject experiences multiple times of a same AE, the number of subject is counted as one when calculating the incidence of the AE.

AEs are summarized in the frequency table based on SOC and PT. The incidence is calculated based on SOC and symptom/sign (the number of cases is counted as number of subjects who have experienced at least one AE).

Severity of AEs and treatment-related adverse events: If a subject experiences multiple times of the same AE, the most severe one will be used in the analysis of the severity of the AE.

A list of cases of AEs and SAEs is provided.

The median time to the onset of the first event is calculated for the adverse events of special interest (AESIs). AESIs include hypertension, proteinuria, hand-and-foot syndrome, hemorrhage, electrocardiogram QT prolonged, and white blood cell count decreased. The specific classification definitions are shown in Appendix 2.

Time to the onset of first event (days) = onset date of first event – date of the first dose + 1

In addition, for the comparisons of the incidences of AEs between the treatment group and the control group, the Fisher's exact method may be used to calculate the P value, which is only used for clinical reference, rather than the deduction of statistical significance.

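### SAP Appendix 2 defines the hemorrhage AESI by a closed term list without hematemesis or positive occult blood, so the grouped bleeding count can be understated

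*SAP*

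**What the plan says.** SAP 7.4.1 sets the AESI categories: "AESIs include hypertension, proteinuria, hand-and-foot syndrome, hemorrhage, electrocardiogram QT prolonged, and white blood cell count decreased". For their content it adds: "The specific classification definitions are shown in Appendix 2". The only AESI-specific analysis it spells out is the median time to first onset, counted from the first dose. Protocol 12.3 also wants AESIs listed and summarized.

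For hemorrhage, SAP Appendix 2 gives 19 preferred terms, the first of which is "Upper gastrointestinal hemorrhage". It has no catch-all entry and no rule for adding terms that turn up in the coded data.

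Protocol 8.3.3 describes bleeding in the gut this way: "Gastrointestinal hemorrhage, including fecal occult blood (++) and above, hematemesis or bloody stool, should be given active symptomatic treatment". It then treats the lower tract separately: "patients with lower gastrointestinal hemorrhage should be given hemostasis, blood transfusion and supportive care".

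The SAP deals with occult blood elsewhere, as a stool test. It is listed in 4.3 and summarized by shift table in 7.4.4, which also reports the proportion of subjects with clinically significant laboratory abnormalities.

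**The concern.** Bleeding is a safety question that readers of this trial will look up. Protocol 4.5.2 supports the 750 mg dose partly with early withdrawals for adverse events in phase II: 9 at 850 mg, "including 4 cases of gastrointestinal hemorrhage", against 3 at 750 mg with no hemorrhage. The grouped hemorrhage category is where a reader would expect to find how many phase III subjects bled and how soon.

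The list does not look narrow by design. It admits symptom-level terms (Hematochezia, Melena, Hemoptysis, Epistaxis) and minor sites (gingival, scleral). By that convention hematemesis belongs on it, and the SAP gives no reason for leaving it out. If bleeds are coded to unlisted terms, the grouped count misses some subjects and dates others too late.

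**Working it through.** The documents state no hemorrhage AESI rate, so there is no figure to reproduce. The check compares terms and then shows what a given loss would do.

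**1. Term comparison.** Each kind of bleeding was looked for among the 19 hemorrhage entries in SAP Appendix 2.

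| Event | Protocol source | Own entry in Appendix 2 | Listed terms that could still catch it |
|---|---|---|---|
| Bloody stool | 8.3.3 | Yes: Hematochezia, Melena | – |
| Hematemesis | 8.3.3 | None | Upper gastrointestinal hemorrhage, if coded that way |
| Occult blood (++) or more | 8.3.3 | None | None directly |
| Lower-GI hemorrhage | 8.3.3 | None | Gastrointestinal hemorrhage, Anal hemorrhage, Hematochezia, Melena |
| Variceal bleeding | Named only as a risk, exclusion criterion 9 | None | Upper gastrointestinal or Gastrointestinal hemorrhage |
| Subarachnoid hemorrhage | Named only as organ damage, 8.3.2 | None | None directly; Cerebral and Brain stem hemorrhage cover other intracranial bleeds |

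Of the three events that 8.3.3 names in describing gastrointestinal hemorrhage, one is listed and two are not.

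**2. Direction.** A subject counts if at least one bleeding event carries a listed term. Adding terms can raise the number of subjects counted or leave it unchanged; it cannot lower it. For a single subject, the recorded first onset can likewise only be too late or missing. The group median is less predictable. Subjects who drop out may have bled early or late, and the SAP does not say how subjects without an event enter the median.

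**3. Size, for illustration only.** Let p be the share of subjects with any bleeding under the wider description, and f the share of those whose bleeding terms are all off the list. Then

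rate counted = p × (1 − f).

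Both p and f are assumptions. The planned apatinib arm is 390 × 2/3 = 260 subjects.

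| p | f = 0 | f = 0.10 | f = 0.25 | f = 0.50 |
|---|---|---|---|---|
| 10% | 10% (26.0) | 9% (23.4) | 7.5% (19.5) | 5% (13.0) |
| 20% | 20% (52.0) | 18% (46.8) | 15% (39.0) | 10% (26.0) |
| 30% | 30% (78.0) | 27% (70.2) | 22.5% (58.5) | 15% (39.0) |

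Parentheses give expected subjects out of 260. At f = 0 nothing is lost.

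**4. Effect on the comparison of arms.** Assume true rates of 15% and 8% and the same f in both arms.

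- f = 0: 15% v 8%, difference 7.0 points, ratio 15/8 = 1.875.
- f = 0.10: 13.5% v 7.2%, difference 6.3 points, ratio 1.875.
- f = 0.30: 10.5% v 5.6%, difference 4.9 points, ratio 1.875.

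With equal f the absolute difference shrinks and the ratio does not move. With unequal f the ratio could move either way.

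**The case against.** The strongest reply is that no loss has been shown. A subject is missed only when every bleeding event is coded off the list, and the documents contain no coded events. The list may have been drawn from terms already seen in blinded data, in which case nothing may be missing. The SAP does not say so, but it does not rule it out. This stands, and it limits the point to a possible understatement.

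The occult blood omission is also weaker than it looks. After screening, Protocol 9.2 calls for the test when stools are abnormal, with hematochezia and melena as its examples. Both are listed terms, so many positives would come from subjects already counted. Whether a positive test is a hemorrhage AESI is a matter of judgement. Laboratory abnormalities do count as adverse events (Protocol 11.1.1, SAP 4.1), so the SAP should still state its choice.

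A reader might infer that the SAP breaches the protocol's AESI definition. It does not. Section 8.3.3 is treatment advice, and the note closing 8.3.5 marks that advice as reference only. The protocol's AESI examples leave hemorrhage out; the SAP added the category. The mismatch is one of scope between two descriptions of bleeding.

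A reader might also infer that bleeding events vanish from the report. They do not. SAP 7.4.1 tabulates all AEs by SOC and PT, analyses severity, and lists AE and SAE cases. It also treats between-arm P values for AEs as clinical reference only, so no formal inference rests on the list. What these tables do not supply is the number of subjects with any bleed, or the time to the first one.

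**Conclusion.** The point holds as a gap in the definition. The hemorrhage AESI rests on a closed list that omits hematemesis and positive occult blood, has no dedicated lower-GI, variceal or subarachnoid term, and has no catch-all. The grouped count can therefore be too low, and a subject's first onset too late or missing, when the only or first bleed carries an unlisted term. The effect on the count runs in one direction. Its size is unknown and may be zero; every rate in the working is an assumption.

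Three stronger readings are not supported:

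- That the bleeding rate will be understated. This needs coded events off the list in subjects with no listed term, and the documents do not show any.
- That the relative comparison of the arms is distorted. This needs different off-list shares by arm, for which there is no evidence.
- That intracranial bleeding is left out altogether. Cerebral and brain stem hemorrhage are listed.

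Severity is low. The primary endpoint is untouched.

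**What to change.** - Define the hemorrhage AESI in Appendix 2 by rule: every coded preferred term denoting bleeding at any site. The present list can stay as examples, with hematemesis and lower-GI, variceal and subarachnoid hemorrhage added at minimum.
- State whether a positive occult blood result reported as an AE counts, and from what level.
- Review the coded terms on blinded data and fix the final list before database lock.

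The cost is one appendix edit and a short blinded term review. The downside is that the reported bleeding rate may rise in both arms.
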